3.6 Neurologic

The following AE terms, regardless of grade, are considered ECIs and should be reported to the Sponsor within 2 business days of the event:

- Autoimmune neuropathy
- Demyelinating polyneuropathy
- Guillain-Barre syndrome
- Myasthenic syndrome

All attempts should be made to rule out other causes such as metastatic disease, other medications or infectious causes. However, the AE should be reported regardless of etiology.

Course of Action

Grade 2 events:

- Report as ECI
- Moderate (Grade 2) – consider withholding pembrolizumab.
- Consider treatment with prednisone 1-2 mg/kg p.o. daily as appropriate
- Consider Neurology consultation. Consider biopsy for confirmation of diagnosis.
- Permanently discontinue for inability to reduce corticosteroid dose to 10 mg or less of prednisone or equivalent per day within 12 weeks.

Grade 3 and 4 events:

- Report as ECI
- Discontinue pembrolizumab
- Obtain neurology consultation. Consider biopsy for confirmation of diagnosis
- Treat with systemic corticosteroids at a dose of 1 to 2 mg/kg prednisone or equivalent once per day. If condition worsens consider IVIG or other immunosuppressive therapies as per local guidelines

When symptoms improve to Grade 1 or less, steroid taper should be started and continued over no less than 4 weeks.

3.7 Ocular

The following AE terms, if considered Grade ≥ 2 or requiring dose modification or use of systemic steroids to treat the AE, is considered an ECI and should be reported to the Sponsor within 2 business days of the event:

- Uveitis

- Iritis

All attempts should be made to rule out other causes such as metastatic disease, infection or other ocular disease (e.g. glaucoma or cataracts). However, the AE should be reported regardless of etiology.

Course of Action

Grade 2 events:

- Evaluation by an ophthalmologist is strongly recommended.
- Treat with topical steroids such as 1% prednisolone acetate suspension and iridocyclitics.
- Discontinue pembrolizumab as per protocol if symptoms persist despite treatment with topical immunosuppressive therapy.

Grade 3 events:

- Evaluation by an ophthalmologist is strongly recommended
- Hold pembrolizumab and consider permanent discontinuation as per specific protocol guidance.
- Treat with systemic corticosteroids such as prednisone at a dose of 1 to 2 mg/kg per day. When symptoms improve to Grade 1 or less, steroid taper should be started and continued over no less than 4 weeks.
- Permanently discontinue for inability to reduce corticosteroid dose to 10 mg or less of prednisone or equivalent per day within 12 weeks.

Grade 4 events:

- Evaluation by an ophthalmologist is strongly recommended
- Permanently discontinue pembrolizumab.
- Treat with corticosteroids as per Grade 3 above

3.8 Renal

The following AEs if \geq Grade 2 are considered ECIs and should be reported to the Sponsor within 2 business days of the event:

- Nephritis
- Nephritis autoimmune
- Renal failure
- Renal failure acute

Creatinine elevations \geq Grade 3 or any grade with dose modification or use of systemic steroids to treat the AE.

All attempts should be made to rule out other causes such as obstructive uropathy, progression of disease, or injury due to other chemotherapy agents. A renal consultation is recommended. However, the AE should be reported regardless of etiology.

Course of Action

Grade 2 events:

- Hold pembrolizumab
- Treatment with prednisone 1-2 mg/kg p.o. daily.
- Permanently discontinue for inability to reduce corticosteroid dose to 10 mg or less of prednisone or equivalent per day within 12 weeks.

Grade 3-4 events:

- Discontinue pembrolizumab
- Renal consultation with consideration of ultrasound and/or biopsy as appropriate
- Treat with systemic corticosteroids at a dose of 1 to 2 mg/kg prednisone IV or equivalent once per day.

When symptoms improve to Grade 1 or less, steroid taper should be started and continued over no less than 4 weeks.

3.9 Skin

Rash and Pruritus

The following AEs should be considered as ECIs, if \geq Grade 3 and should be reported to the Sponsor within 2 business days of the event:

- Pruritus
- Rash
- Rash generalized
- Rash maculo-papular
- In addition to CTCAE Grade 3 rash, any rash that is considered clinically significant, in the physician's judgment, should be treated as an ECI. Clinical significance is left to the physician to determine, and could possibly include rashes

such as the following:

- rash with a duration >2 weeks; OR
- rash that is >10% body surface area; OR
- rash that causes significant discomfort not relieved by topical medication or temporary cessation of study drug.

Other Skin ECIs

The following AEs should **always** be reported as ECIs, regardless of grade, and should be reported to the Sponsor within 2 business days of the event:

- Dermatitis exfoliative
- Erythema multiforme
- Steven's Johnson syndrome
- Toxic epidermal necrolysis

Please note, the AE should be reported regardless of etiology.

Course of Action

Grade 2 events:

- Symptomatic treatment should be given such as topical glucocorticosteroids (e.g., betamethasone 0.1% cream or hydrocortisone 1%) or urea-containing creams in combination with oral anti-pruritics (e.g., diphenhydramine HCl or hydroxyzine HCl).
- Treatment with oral steroids is at physician's discretion for Grade 2 events.

Grade 3 events:

- Hold pembrolizumab.
- Consider Dermatology Consultation and biopsy for confirmation of diagnosis.
- Treatment with oral steroids is recommended, starting with 1 mg/kg prednisone or equivalent once per day or dexamethasone 4 mg four times orally daily. When symptoms improve to Grade 1 or less, steroid taper should be started and continued over no less than 4 weeks.
- Permanently discontinue for inability to reduce corticosteroid dose to 10 mg or less of prednisone or equivalent per day within 12 weeks.

Grade 4 events:

- Permanently discontinue pembrolizumab.
- Dermatology consultation and consideration of biopsy and clinical dermatology photograph.
- Initiate steroids at 1 to 2 mg/kg prednisone or equivalent. When symptoms improve to Grade 1 or less, steroid taper should be started and continued over no less than 4 weeks.

3.10 Immediate Evaluation for Potential Skin ECIs

A. Photographs:

Every attempt should be made to get a photograph of the actual ECI skin lesion or rash as soon as possible. **Obtain appropriate consent for subject photographs if a consent form addendum is required by your IRB/ERC.**

- Take digital photographs of:
 - the head (to assess mucosal or eye involvement),
 - the trunk and extremities, and
 - a close-up of the skin lesion/rash.
- If possible, a ruler should be placed alongside the site of a skin occurrence as a fixed marker of distance.
- The time/date stamp should be set in the 'ON' position for documentation purposes.
- Photographs should be stored with the subject's study records.
- The Sponsor may request copies of photographs. The local study contact (e.g., CRA) will provide guidance to the site, if needed.

B. Past Medical History:

Collect past medical history relevant to the event, using the questions in Appendix 2 (Past Medical History Related to Dermatologic Event) as a guide. Any preexisting conditions not previously reported (e.g., drug allergy) should be entered into the Medical History eCRF.

C. Presentation of the Event:

Collect information on clinical presentation and potential contributing factors using the questions in Appendix 3 (Presentation of the Dermatologic Event) as a guide. This information should be summarized and entered in narrative format in the AE eCRF. Please use the available free-text fields, such as Signs and Symptoms. Note pertinent negatives where applicable to reflect that the information was collected. Any treatments administered should be entered on the Concomitant Medication eCRF.

D. Vital Signs and Standard Laboratory Tests:

Measure vital signs (pulse, sitting BP, oral temperature, and respiratory rate) and record on the Vital Signs eCRF. Perform standard laboratory tests (CBC with manual differential and serum chemistry panel, including LFTs).

E. Focused Skin Examination:

Perform a focused skin examination using the questions in Appendix 4 (Focused Skin Examination) as a guide. Information should be summarized and entered on the Adverse Experience eCRF as part of the narrative.

F. Dermatology Consult

Refer the subject to a dermatologist as soon as possible.

- For a “**severe rash**”, the subject must be seen within **1-2 days** of reporting the event.
- For **clinically significant rash**, the subject should be seen within **3-5 days**.

The dermatologist should submit a biopsy sample to a certified dermatopathology laboratory or to a pathologist experienced in reviewing skin specimens.

The site should provide the dermatologist with all relevant case history, including copies of clinical photographs and laboratory test results.

3.11 Other

The following AEs, regardless of grade, are considered ECIs and should be reported to the Sponsor within 2 business days of the event:

- Myocarditis
- Pericarditis
- Pancreatitis
- Any additional Grade 3 or higher event which the physician considers to be immune related

All attempts should be made to rule out other causes. Therapeutic specialists should be consulted as appropriate. However, the AE should be reported regardless of etiology.

Course of Action

Grade 2 events or Grade 1 events that do not improve with symptomatic treatment:

- Withhold pembrolizumab.
- Systemic corticosteroids may be indicated.
- Consider biopsy for confirmation of diagnosis.
- If pembrolizumab held and corticosteroid required, manage as per grade 3 below.

Grade 3 events:

- Hold pembrolizumab
- Treat with systemic corticosteroids at a dose of 1 to 2 mg/kg prednisone or equivalent once per day.
- When symptoms improve to Grade 1 or less, steroid taper should be started and continued over no less than 4 weeks.
- Permanently discontinue for inability to reduce corticosteroid dose to 10 mg or less of prednisone or equivalent per day within 12 weeks. Otherwise, pembrolizumab treatment may be restarted and the dose modified as specified in the protocol

Grade 4 events:

- Treat with systemic corticosteroids at a dose of 1 to 2 mg/kg prednisone or equivalent once per day.
- Discontinue pembrolizumab

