	Grade 3 ^b or 4 ^c	Permanently discontinue	
 Administer corticosteroids (initial dose of 1-2 mg/kg prednisone or equivalent) followed by taper 	
Type 1 diabetes mellitus (T1DM) or Hyperglycemia	Newly onset T1DM or Grade 3 or 4 hyperglycemia associated with evidence of β -cell failure	Withhold ^d	
 Initiate insulin replacement therapy for participants with T1DM Administer anti-hyperglycemic in participants with hyperglycemia 	
 Monitor participants for hyperglycemia or other signs and symptoms of diabetes.
Hypophysitis	Grade 2	Withhold	
 Administer corticosteroids and initiate hormonal replacements as clinically indicated. 	
 Monitor for signs and symptoms of hypophysitis (including hypopituitarism and adrenal insufficiency)
	Grade 3 or 4	Withhold or permanently discontinue ^d		
Hyperthyroidism	Grade 2	Continue	
 Treat with nonselective beta-blockers (eg, propranolol) or thionamides as appropriate 	
 Monitor for signs and symptoms of thyroid disorders.
	Grade 3 or 4	Withhold or permanently discontinue ^d		
Hypothyroidism	Grade 2-4	Continue	
 Initiate thyroid replacement hormones (eg, levothyroxine or liothyroinone) per standard of care 	
 Monitor for signs and symptoms of thyroid disorders.

Nephritis grading according to increased creatinine or acute kidney injury	Grade 2	Withhold	
 Administer corticosteroids (prednisone 1 to 2 mg/kg or equivalent) followed by taper. 	
 Monitor changes of renal function
	Grade 3 or 4	Permanently discontinue		
Neurological Toxicities	Grade 3 or 4	Permanently discontinue	
 Based on severity of AE administer corticosteroids 	
 Ensure adequate evaluation to confirm etiology and/or exclude other causes
Myocarditis	Grade 1	Withhold	
 Based on severity of AE administer corticosteroids 	
 Ensure adequate evaluation to confirm etiology and/or exclude other causes
	Grade 2, 3 or 4	Permanently discontinue		

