Exfoliative Dermatologic Conditions	Suspected SJS, TEN, or DRESS	Withhold	
 Based on severity of AE administer corticosteroids 	
 Ensure adequate evaluation to confirm etiology or exclude other causes
	Confirmed SJS, TEN, or DRESS	Permanently discontinue		
All other irAEs	Persistent Grade 2	Withhold	
 Based on type and severity of AE administer corticosteroids 	
 Ensure adequate evaluation to confirm etiology and/or exclude other causes
	Grade 3	Withhold or discontinue based on the type of event ^a .		
	Grade 4 or recurrent Grade 3	Permanently discontinue		

AE(s)=adverse event(s); ALT= alanine aminotransferase; AST=aspartate aminotransferase; CTCAE=Common Terminology Criteria for Adverse Events; DRESS=Drug Rash with Eosinophilia and Systemic Symptom; GI=gastrointestinal; IO=immuno-oncology; ir=immune related; IV=intravenous; SJS=Stevens-Johnson Syndrome; T1DM=type 1 diabetes mellitus; TEN=Toxic Epidermal Necrolysis; ULN=upper limit of normal.

Note: Non-irAE will be managed as appropriate, following clinical practice recommendations.

^a AST/ALT: >3.0 to 5.0 x ULN if baseline normal; >3.0 to 5.0 x baseline, if baseline abnormal; bilirubin: >1.5 to 3.0 x ULN if baseline normal; >1.5 to 3.0 x baseline if baseline abnormal

^b AST/ALT: >5.0 to 20.0 x ULN, if baseline normal; >5.0 to 20.0 x baseline, if baseline abnormal; bilirubin: >3.0 to 10.0 x ULN if baseline normal; >3.0 to 10.0 x baseline if baseline abnormal

^c AST/ALT: >20.0 x ULN, if baseline normal; >20.0 x baseline, if baseline abnormal; bilirubin: >10.0 x ULN if baseline normal; >10.0 x baseline if baseline abnormal

^d The decision to withhold or permanently discontinue pembrolizumab is at the discretion of the investigator or treating physician. If control achieved or \leq Grade 2, pembrolizumab may be resumed.

^e Events that require discontinuation include, but are not limited to: encephalitis and other clinically important irAEs (e.g., vasculitis and sclerosing cholangitis).

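### Table 3 and ECI guidance 3.11 give different dosing instructions for myocarditis at Grades 2 and 3 (and by implication Grade 1); confirmed SJS/TEN shows a weaker, implied mismatch with 3.9

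*Combined protocol and SAP*

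**What the plan says.** **Myocarditis, Table 3 (Section 5.2.1.2).** The row has two entries: "Myocarditis Grade 1 Withhold" and "Grade 2, 3 or 4 Permanently discontinue".

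**Myocarditis, ECI guidance 3.11 (Section 11.5).** Myocarditis is the first event listed, at any grade. Withholding applies under the heading "Grade 2 events or Grade 1 events that do not improve with symptomatic treatment". Within that block, "If pembrolizumab held and corticosteroid required, manage as per grade 3 below". At Grade 3 the instruction is to hold, with permanent discontinuation if the steroid dose cannot be brought down within 12 weeks. The text then continues: "Otherwise, pembrolizumab treatment may be restarted and the dose modified as specified in the protocol". At Grade 4 the drug is discontinued.

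**Confirmed SJS/TEN, Table 3.** "Confirmed SJS, TEN, or DRESS Permanently discontinue", with no reference to grade.

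**SJS/TEN, ECI guidance 3.9.** Both events are in the list introduced by "The following AEs should always be reported as ECIs, regardless of grade". One course of action by grade follows the skin lists. Grade 3 is a hold, qualified by "Permanently discontinue for inability to reduce corticosteroid dose to 10 mg or less of prednisone or equivalent per day within 12 weeks". Grade 4 is permanent discontinuation.

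**Which text governs.** The overview of the guidance tells the physician to follow the protocol's language on dose modification. Its next subsection says that the guidance itself directs when to hold or discontinue for each immune-related event, and defines a hold as a stop after which resumption may be considered.

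**The concern.** The guidance is a numbered appendix of this protocol, so both texts carry protocol status. For the same event at the same grade, one ends treatment for good and the other leaves a route back to it. Whether a patient with Grade 2 or 3 myocarditis may be re-exposed should not depend on which of the two a site is reading.

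There is also a consequence for the data. Section 5.6 requires discontinuation for unacceptable adverse experiences as set out in Section 5, so a restart that 3.11 permits could be classed as a protocol deviation. Section 8.3.2.4 tabulates adverse events requiring discontinuation separately, and that count would depend on which text was applied.

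**Working it through.** No sample size, power or other figure is involved, so the check sets the texts side by side.

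| Event and grade | Table 3 | ECI guidance | Agree? |
|---|---|---|---|
| Myocarditis, Grade 1 | Withhold, no condition | 3.11: withhold if not improving with symptomatic treatment; silent otherwise | No, by implication |
| Myocarditis, Grade 2 | Permanently discontinue | 3.11: withhold; if steroids are needed, handle as Grade 3 | No |
| Myocarditis, Grade 3 | Permanently discontinue | 3.11: hold; restart possible if steroids can be reduced within 12 weeks | No |
| Myocarditis, Grade 4 | Permanently discontinue | 3.11: discontinue (defined in the guidance as permanent) | Yes |
| Confirmed SJS/TEN, Grade 3 | Permanently discontinue | 3.9: hold; permanent only if steroids cannot be reduced within 12 weeks | No, by implication |
| Confirmed SJS/TEN, Grade 4 | Permanently discontinue | 3.9: permanently discontinue | Yes |

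Four checks on whether the differences are only apparent:

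1. *Scope.* Table 3 covers drug-related events. The guidance says its management advice applies when the physician judges the event related to pembrolizumab. The two therefore address the same cases.
2. *Footnotes.* Footnote d of Table 3 gives the investigator discretion and allows resumption. It is attached to endocrine rows, not to the myocarditis row, so it does not bring Table 3 into line with 3.11.
3. *Reach of the restart sentence.* It stands in the Grade 3 block of 3.11, but held Grade 1 and 2 events that need steroids are sent to that block. Restart is therefore available at Grade 2 too, where Table 3 rules it out.
4. *Strength of the skin comparison.* Section 3.9 has no restart sentence. Possible resumption at Grade 3 follows from two things together: the definition of a hold, and the fact that permanent discontinuation is tied to failure of the steroid reduction. The comparison is limited to SJS and TEN, because 3.9 does not list DRESS.

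**The case against.** The strongest reply is that the documents already set an order of precedence. The guidance overview calls its recommendations guidelines and defers to the protocol on dose modification. Section 5.2.1.2 makes Table 3 mandatory for withholding and cites the guidance for supportive care. Section 5.4.1 also uses the guidance for supportive-care detail and sends dose modification back to Section 5.2.1. The restart sentence in 3.11 itself refers to the protocol. In addition, Table 6 in Section 7.2.4 requires advance approval before rechallenge after a serious event that the drug may have caused.

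Much of this stands. A reader might infer that the protocol gives a site no way to tell which text governs; these cross-references do not support that, and they point dosing questions to Table 3. What they do not do is make the two texts agree:

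- The guidance also presents itself as the specific direction on when to hold or discontinue.
- Section 7.1.2.1 sends sites to it for management of possible immune-related events, and Section 7.2.3.2 does so for management of ECIs. Section 5.4.1 has no myocarditis or skin entry of its own, so the event-specific advice sits in 3.11 and 3.9.
- Where the guidance defers on a particular event, it says so on the spot, as in 3.4 and 3.7. The hold lines of 3.11 and 3.9 carry no such pointer. In 3.11 the reference to the protocol follows the permission to restart and most naturally governs how the dose is modified.
- The rechallenge approval in Table 6 is itself tied to the protocol's dose-modification guidelines, which leads back to the same question.

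Two further points are accepted. Grade 1 myocarditis is a weaker difference, because 3.11 never says to continue dosing when the event improves. The effect on the safety tables cannot be estimated, since the documents give no expected frequency of these events.

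**Conclusion.** The myocarditis contradiction is in the text. At Grades 2 and 3, permanent discontinuation stands against withholding or holding with a possible restart. Grade 1 differs by implication and Grade 4 agrees. For confirmed SJS/TEN the mismatch at Grade 3 is secondary and implied. The deference clauses reduce the practical risk without removing the conflict.

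Three stronger readings should not be drawn:

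- *SJS/TEN presents the same conflict as myocarditis.* It does not: 3.9 contains no restart sentence.
- *Grade 2 SJS/TEN would be dosed without interruption under 3.9.* The Grade 2 text there reads as care for rash and itching. The documents only link to the CTCAE (Section 11.2), so whether these events can be Grade 2 cannot be checked from them.
- *A patient might receive 17 more doses under one text and none under the other.* That is only the ceiling 18 − 1 = 17. It ignores the hold, the steroid taper of at least 4 weeks, and the disease-status conditions for continuing treatment in Sections 2.1 and 7.1.5.2.

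On the data side, if all 33 planned patients are treated, each case classified differently moves the proportion discontinuing for an adverse event by 1/33 = 3.0 percentage points. How many such cases would arise is unknown. The argument for acting is the safety of the individual patient, not a measurable shift in the analysis.

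**What to change.** Reconcile guidance 3.11 and 3.9 with the myocarditis and exfoliative-skin rows of Table 3. Each event and grade should carry a single instruction on hold, permanent discontinuation and restart, with identical text in both places. For Grade 1 myocarditis, state explicitly whether withholding depends on improvement. For confirmed SJS/TEN, state whether the grade-based course in 3.9 applies. Which instruction is correct is for the sponsor-investigator and clinical team to decide; this review does not propose one.

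The cost is a protocol wording amendment and a notice to sites. The design, sample size and analyses do not change.

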3.12 Infusion Reactions

The following AE terms, regardless of grade, are considered ECIs and should be reported to the Sponsor within 2 business days of the event:

- Allergic reaction
- Anaphylaxis
- Cytokine release syndrome
- Serum sickness
- Infusion reactions
- Infusion-like reactions

Course of Action

Refer to infusion reaction table in the protocol and below.

NCI CTCAE Grade	Treatment	Premedication at Subsequent Dosing
Grade 1 Mild reaction; infusion interruption not indicated; intervention not indicated	Increase monitoring of vital signs as medically indicated until the subject is deemed medically stable in the opinion of the investigator.	None

Grade 2 Requires infusion interruption but responds promptly to symptomatic treatment (e.g., antihistamines, NSAIDS, narcotics, IV fluids); prophylactic medications indicated for <=24 hrs	
Stop Infusion.
 
Additional appropriate medical therapy may include but is not limited to:
 
 IV fluids Antihistamines NSAIDS Acetaminophen Narcotics 
Increase monitoring of vital signs as medically indicated until the subject is deemed medically stable in the opinion of the investigator.
 
If symptoms resolve within one hour of stopping drug infusion, the infusion may be restarted at 50% of the original infusion rate (e.g. from 100 mL/hr to 50 mL/hr).
 
Otherwise dosing will be held until symptoms resolve and the subject should be premedicated for the next scheduled dose.
 
Subjects who develop Grade 2 toxicity despite adequate premedication should be permanently discontinued from further trial treatment administration.
	Subject may be premedicated 1.5h (\pm 30 minutes) prior to infusion of pembrolizumab with: Diphenhydramine 50 mg p.o. (or equivalent dose of antihistamine). Acetaminophen 500-1000 mg p.o. (or equivalent dose of antipyretic).
Grades 3 or 4 Grade 3: Prolonged (i.e., not rapidly responsive to symptomatic medication and/or brief interruption of infusion); recurrence of symptoms following initial improvement; hospitalization indicated for other clinical sequelae (e.g., renal impairment, pulmonary infiltrates) Grade 4: Life-threatening; pressor or ventilatory support indicated	
Stop Infusion.
 
Additional appropriate medical therapy may include but is not limited to:
 
 IV fluids Antihistamines NSAIDS Acetaminophen Narcotics Oxygen Pressors Corticosteroids Epinephrine 
Increase monitoring of vital signs as medically indicated until the subject is deemed medically stable in the opinion of the investigator.
 
Hospitalization may be indicated. Subject is permanently discontinued from further trial treatment administration.
	No subsequent dosing
Appropriate resuscitation equipment should be available in the room and a physician readily available during the period of drug administration. For Further information, please refer to the Common Terminology Criteria for Adverse Events v4.0 (CTCAE) at http://ctep.cancer.gov		

Infusion Reactions

